9.1. Subject Disposition and Withdrawals

All individuals who sign the ICF will be included in disposition summary. The number of subjects who are screened, screen failed with reasons, randomized, number of subjects in each analysis set, number of subjects who excluded from each analysis set (including reasons for exclusion), number of subjects who completed the study treatment, who discontinued the treatment with reasons for treatment discontinuation, number of subjects who discontinued the study treatment but remained in the study [REDACTED], number of subjects who completed the study [REDACTED], [REDACTED], who discontinued from the study with reasons for study discontinuation, death will be summarized by treatment group. All disposition data will be listed by subject and treatment group.

9.2. Protocol Deviations

Protocol deviations will be identified throughout the trial following the 'Protocol Deviation and Noncompliance Management Plan' [REDACTED]. Final definition of protocol deviations, categorization of protocol deviations into important / non-important, determination whether an important protocol deviation has an impact on the assessment of efficacy, and the determination of the populations will be finalized in the BDRM following [REDACTED] prior to database lock and unblinding.

All protocol deviations identified during the conduct of the trial will be listed, while only the important protocol deviations will be summarized by deviation category using the ITT population. The list of protocol deviations will be reviewed by the Sponsor, the medical monitor, and the study statistician and finalized before database lock. Exclusions from the PP population, if any, along with the rationale for the exclusion will be recorded in the protocol deviation file.

Important protocol deviations which potentially impact efficacy measurement will lead to exclusion from the PP population.

9.3. Demographic and Baseline Characteristics

Descriptive summaries of demographic and baseline characteristics will be provided using the ITT population. These tabulations will include the following variables:

- Age (years)
- Age group
- Gender
- Subject's child bearing potential
- Race
- Weight (kg)
- Alcohol consumption history
- Smoking history

[REDACTED]

[REDACTED]

[REDACTED]

This document is confidential.

All demographic and baseline characteristics data will be listed by subject.

9.4. Medical History and Concomitant Illnesses

Medical history will include any pre-existing conditions, including AIS (the primary disease) as well as all prior significant illnesses, up to and including 1 year before Screening (Visit 1). Additional pre-existing conditions present at the time when informed consent is given and up to the time of the initiation of dosing [REDACTED] will be regarded as concomitant illnesses. All recorded medical history and concomitant illnesses verbatim terms will be coded using Medical Dictionary for Regulatory Activities (MedDRA).

Medical history and concomitant illnesses data will be summarized by system organ class (SOC) and preferred term (PT) using the ITT population. Subject listings of medical history, concomitant illnesses, alcohol consumption history and smoking history will also be provided.

9.5. Medications

All recorded non-study medications will be coded using the dynamic version of the World Health Organization Drug Dictionary (WHODrug) Global B3 Mar 2025. WHODrug coding includes the Anatomical Therapeutic Chemical (ATC) classification levels and preferred name. All medications will be classified according to the study period in which its use occurred (i.e., Prior or Concomitant).

9.5.1. Prior Medication

All medications stopped before the 1st IP will be considered as prior medications. The incidence of prior medication use will be summarized by ATC level terms and preferred names using the ITT population.

9.5.2. Concomitant Medication

All medications started on the day of the 1st IP or afterwards and medications started prior to the 1st IP but continued after start of IP dose are considered as concomitant medications. Concomitant medications will be summarized by ATC level terms and preferred names using the ITT population.

Any medication reported more than one time will only be counted once per subject for each preferred name. All prior and concomitant medication use data will be listed by subject.

In case of incomplete stop date, the medication will be considered as prior only if this can be concluded without any doubt. All other cases of incomplete or missing stop dates will be considered concomitant medications.

9.5.3. Other Therapies

A listing of surgical procedures as captured in the CRF will be provided.

9.6. Study Drug Exposure

The total number of subject dosed, cumulative dose number, cumulative dose administered, planned cumulative dose (mg), relative dose intensity (%), relative dose intensity category and subject with at least one interrupted infusion, will be summarized descriptively for all subjects in safety population by treatment group. Also, all study drug administration data will be listed by subject.

This document is confidential.

10. Efficacy

All efficacy endpoints will be summarized and analyzed using the ITT population. Additionally, supportive analyses will be performed on the PP population and on the Completers population. Comprehensive listings of all efficacy data will also be presented by subject and visit.

All efficacy endpoints will be summarized using descriptive statistics by treatment group and by visit, as appropriate. Categorical endpoints will be summarized by treatment group by presenting the number and percentage of subjects in each category.

This is an exploratory study, i.e., all statistical comparison between the treatment groups is not of confirmatory but of descriptive nature. The statistical comparison of the efficacy endpoints based on mRS and NIHSS between treatment groups will be performed either after multiple imputation (MI) of missing data or will be analyzed

For all other efficacy endpoints missing data will not be imputed prior statistical comparison, i.e. summaries and statistical analysis will use the observed data within ITT only.

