### 11.1 Modified Rankin Scale

The mRS measures the degree of disability or dependence in the daily activities of patients who have suffered a stroke. The scale runs from 0 (perfect health without symptoms) to 6 (dead).

The score and corresponding

description for the mRS is provided in [Appendix 2](#).

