6.5. Completers Population

All ITT subjects who are treated and complete study procedures through Day 90 without a major protocol deviation potentially impacting efficacy measurement [REDACTED]. The Completers population will be used as supportive basis for analysis of efficacy [REDACTED]

This document is confidential.

7. Estimands

Estimands approach is not applicable as this is an exploratory trials.

This document is confidential.

8. General Aspects for Statistical Analysis

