8.3. Missing Data

Missing data will be imputed for the efficacy variables mRS and NIHSS as described in [Section 10.1](#).

Missing or incomplete dates in safety data: In all listings, missing or incomplete dates will be left as they have been recorded. However, for calculation and sorting based on dates and for consideration in summary tables, the following method will be used: The most conservative approach will be systematically considered. For example, if the onset date of an AE/concomitant medication is missing or incomplete, it is assumed to have occurred during the study treatment, except if the partial onset date indicates differently. A missing/incomplete date of medical history or disease diagnosis will be assumed to have occurred before any study treatment.

Missing TEAE relationship will be imputed by 'related' for summary tables.

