10.2.2. Montreal Cognitive Assessment (MoCA)

The MoCA total score and subscale will be summarized

This document is confidential.

[figure not shown]

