10.2.3. Change of infarct volume [REDACTED] from Baseline by MRI/CTP

The absolute and percentage change from baseline of infarct volume in MRI or CTP examination will be presented [REDACTED] by treatment group on observed ITT. Comparisons between treatments will be performed on observed ITT [REDACTED]

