10.2.6. Proportion of subjects with 90% reduction in hypoperfusion lesion [REDACTED]
[REDACTED] from Baseline:

The number and percentage of subjects showing 90% reduction in hypoperfusion lesion [REDACTED]
[REDACTED] will be summarized by treatment group. The difference of the
proportions between the treatment groups and the corresponding 95% CIs will be presented.
Comparisons between treatment groups will be made on the observed data using the Chi-square test
[REDACTED].

[REDACTED]

This document is confidential.

11. Safety

Safety analyses will be performed on the Safety population.

Safety will be assessed based on the incidence of AEs and changes in laboratory results, vital signs, and ECG parameters. For repeated safety assessments collected at scheduled time points, the last non-missing pre-dose value will be used as baseline, and the first non-missing value at each post-dose time points will be used in the analyses. However, all pre- and post-dose assessments including repeat assessments will be presented in data listings. Data collected at unscheduled visits will be included in data listings but will not be considered for analyses.

All safety summaries and analyses will be performed using observed data on the Safety population without imputation of any missing safety data.

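### MoCA is compared only among subjects with a score, so deaths and untestable subjects drop out and the arm with more deaths can look better; the concern is weaker for imaging

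*SAP*

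**What the plan says.** SAP 8.3 sets the scope of imputation: "Missing data will be imputed for the efficacy variables mRS and NIHSS as described in" section 10.1. The opening of SAP section 10 gives the rule for everything else: "For all other efficacy endpoints missing data will not be imputed prior statistical comparison", and "summaries and statistical analysis will use the observed data within ITT only".

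The rule is repeated for two imaging endpoints. For infarct volume (SAP 10.2.3): "Comparisons between treatments will be performed on observed ITT". For the 90% hypoperfusion reduction (SAP 10.2.6): "Comparisons between treatment groups will be made on the observed data using the Chi-square test". For cognition (SAP 10.2.2) the visible text is only "The MoCA total score and subscale will be summarized", followed by redaction, so the general rule is the only one that can be read.

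SAP section 7 defines no strategy for death: "Estimands approach is not applicable as this is an exploratory trials". Protocol 11.1 and 11.2 give death a score on the mRS (6) and the NIHSS (42). Protocol 11.3 gives MoCA a range of 0 to 30, with no value for death.

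**The concern.** SAP 6.3 defines the ITT population as everyone randomized, whatever happens afterwards. An analysis of those with a recorded MoCA is a subset of that population, selected by events after randomization. If treatment affects who survives or who can be tested, the two subsets are no longer comparable. If those lost would have scored badly, the arm that loses more of them shows the higher mean.

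Such losses are foreseeable, since the trial enrols NIHSS 4 to 25. The supportive analyses do not help. SAP 6.4 and 6.5 require completion through Day 30 or Day 90, so they also remove subjects who die before those days.

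At stake is the reading of a secondary result. A modest cognitive difference in a Phase II trial could be taken as support for further development when it reflects only who remained to be tested.

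**Working it through.** The plan has no figure of its own to reproduce. The sample-size sections are not visible, and the documents give no MoCA SD, missing rate or correlation for this trial. Those inputs are assumptions.

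**Inputs**
- About 200 subjects randomized 1:1, so 100 per arm (Protocol 7.1, SAP 4.1).
- Assumed: no true effect on MoCA; normal scores; SD 4 or 6; missing 5% v 10%, or 10% v 20%.
- Illustrative missing rates of 6.25% v 12.5%, the death rates in the earlier single-dose stroke study (Protocol 5.3: one death per arm; the percentages imply 1/16 and 1/8). One death per arm says nothing about direction.

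**MoCA mean.** If the lowest fraction d of a normal score is missing, the observed mean rises by SD × φ(z_d)/(1 − d), where z_d is the d-quantile. If missingness has correlation ρ with the score, the rise is multiplied by ρ.
- d = 5%: φ/(1 − d) = 0.109. d = 10%: 0.195. Difference 0.086 SD.
- SD 6: 0.086 × 6 = 0.52 points with ρ = 1, 0.26 with ρ = 0.5, and 0 with ρ = 0.
- Standard error: 6 × √(1/95 + 1/90) = 0.88.

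| Missing | SD | ρ = 0 | ρ = 0.5 | Lowest scorers missing | SE |
|---|---|---|---|---|---|
| 5% v 10% | 4 | 0 | 0.17 | 0.35 | 0.59 |
| 5% v 10% | 6 | 0 | 0.26 | 0.52 | 0.88 |
| 6.25% v 12.5% | 6 | 0 | 0.31 | 0.62 | 0.89 |
| 10% v 20% | 6 | 0 | 0.46 | 0.93 | 0.92 |

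All differences favour the arm with more missing.

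**Effect of ranking death worst.** A simulation used 4,000 runs, 100 per arm, SD 6, ρ = 0.5, and 6.25% (arm A) v 12.5% (arm B) missing, all treated as deaths. On observed data B is ahead by 0.31 points, and the probability that a subject in B outscores one in A is 0.515. With death ranked lowest that probability is 0.481, so the direction reverses.

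**90% hypoperfusion reduction.** Suppose 40 true responders per 100 in each arm and every missing subject a non-responder.
- 6.25% v 12.5% missing: 40/93.75 = 42.7% v 40/87.5 = 45.7%, a spurious 3.0 points.
- 0.5% v 2% missing, closer to an early scan: 40/99.5 = 40.2% v 40/98 = 40.8%, a spurious 0.6 points (0.5 to 0.8 for true rates of 30% to 50%).
- Counting those missing as non-responders returns 40% v 40%.

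**The case against.** The strongest reply is that the trial already shows what a reader needs. All-cause mortality to Day 90 is tabulated by arm (SAP 11.2.3), and deaths appear in disposition (SAP 9.1). The mRS, which scores death, is tabulated by category (SAP 10.1.1). Summaries of continuous variables give n by arm (SAP 8.1), headers give N (SAP 16.2.4), and a missing category is added to tables (SAP 16.2.5.2). All comparisons are declared exploratory. This stands as a limit on severity. It does not repair the comparison: a separate mortality table does not adjust a survivors-only mean, and a single missing category does not separate death from untestable or other reasons.

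The size is also uncertain. The model truncates a score, while the endpoint is change from baseline, and the documents do not show that the lowest scorers would have the worst change. A subject untestable before dosing is lost through a pre-treatment characteristic, which does not bias the arms in this way. Both points stand, so the figures are illustrations.

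A reader might infer that the same problem applies equally to infarct and perfusion endpoints. The documents do not support that. The one visible imaging time is 24 hours, for infarct volume (Protocol synopsis). Few deaths would be expected by then, and nothing shows that missing scans are mainly deaths; at that time inability to be scanned would be the main route.

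A reader might also infer that the plan contains no sensitivity analysis for death. Parts of SAP 10.2.2 to 10.2.6 are redacted, so only the visible text can be judged.

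**Conclusion.** The concern holds for MoCA. The stated rule yields a comparison of testable survivors, the supportive populations share the defect, and no other handling is visible. Under SD 6 and 10% v 5% missing, the spurious difference lies between 0 and 0.52 points, about 0.26 at correlation 0.5. Each of these is below the standard error of about 0.9, so this mechanism alone would seldom produce a convincing result, though it can shift or reverse a small one.

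It would go too far to say that harm on survival will appear as cognitive benefit. That requires unequal losses, and that those lost would have scored worse. The primary safety endpoint is unaffected. For imaging the point is weaker and depends on scan times that are mostly redacted.

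**What to change.** Keep the observed-data analysis as the main one. Before unblinding, add to the SAP:

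1. For MoCA, one sensitivity analysis that ranks deaths worst and subjects recorded as untestable because of stroke severity next worst, compared by a rank test stratified by the randomization factors. The visible text does not show that this reason is collected; if it is not, rank deaths only.
2. For the 90% hypoperfusion reduction, a sensitivity analysis that counts death before the scan as non-response.
3. Beside each MoCA and imaging comparison, the number without a value by arm and by reason: death, untestable, other.

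The cost is a short SAP paragraph for each analysis, one extra table for each of the two endpoints, and added rows in existing tables. It rises if the reason for a missing MoCA has to be retrieved from the sites. The composite mixes death with the measure, and a death unrelated to the stroke lesion counts as the worst result, so it is supportive only. If the redacted text already contains such an analysis, the sponsor need only confirm it.

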10.1. Efficacy Endpoints for mRS and NIHSS and Analysis

10.1.1. Analysis of functional outcome based on mRS assessments

All binary response variables defined on mRS assessments at the respective visits will be summarized with the number and percentage of subjects with and without response by treatment group considering observed data of ITT. The difference of the proportions based on observed data of ITT between the treatment groups with the corresponding 95% confidence intervals (CIs) will be presented for the defined time points.

Comparison between the treatment groups will be performed for the binary response variables using the Chi-square test at each defined timepoint separately and additionally

Additionally, the comparison between the treatment groups at each timepoint and overall will be performed for the binary response

The model will be performed for both categorizations of mRS, i.e., subjects with mRS ≤ 2 and subjects with mRS ≤ 1

This document is confidential.

The number and percentage of subjects in each score category of mRS will be presented for baseline and for the post-baseline time points [REDACTED] by treatment group for observed ITT population. A shift table will be presented by treatment with shifts from baseline to each defined post-baseline time point [REDACTED]

[REDACTED]

The [REDACTED] steps are described in section 10.1.3.

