10.1.2. Analysis of neurological outcome based on NIHSS assessments

All binary response variables defined on NIHSS assessments at the respective visits will be summarized with the number and percentage of subjects with and without response by treatment group considering observed data of ITT. The difference of the proportions based on observed data of ITT between the treatment groups with the corresponding 95% CIs will be presented for the defined time points.

Comparison between the treatment groups will be performed for the defined binary response variables using the Chi-square test [REDACTED] at each defined timepoint separately and additionally, [REDACTED]

[REDACTED]

Additionally, the comparison between the treatment groups at each timepoint and overall will be performed for the binary response variables [REDACTED]

[figure not shown]
[REDACTED]

The total score, subscores and change from baseline in NIHSS will be summarized at each defined time point by treatment group and overall on observed data of ITT [REDACTED]

[REDACTED]

This document is confidential.

Comparison between the treatment groups will be performed for the continuous change from baseline variable [REDACTED] for each defined time point separately, [REDACTED]

The [REDACTED] are described in section 10.1.3.

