10.1.3. General Multiple Imputation Approach

The primary analysis approach for mRS and NIHSS efficacy endpoints will consider the multiple imputation (MI) of missing data [REDACTED]

This document is confidential.

[REDACTED]

[REDACTED]

[REDACTED]

This document is confidential.

10.1.4. Supportive analyses:

The main analysis will be repeated on the PP and Completers populations as supportive analyses.

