- Percentage values will be printed to one decimal place, in parentheses with no spaces, one space after the count (e.g., 7 (12.8), 13 (5.4)). Unless otherwise noted, for all percentages, the number of subjects in the analysis set for the treatment group who have an observation will be the denominator. Percentages after zero counts will not be displayed and percentages equating to 100% will be presented as 100%, without decimal places.
- Tabular display of data for medical history, prior/concomitant medications, and all tabular displays of adverse event data will be presented by the body system, treatment class, or SOC with the highest occurrence in the active treatment group in decreasing order, assuming all terms are coded. Within the body system, drug class and SOC, medical history (by preferred term), drugs (by ATC1 code), and adverse events (by preferred term) will be displayed in decreasing order. If incidence for more than 1 term is identical, they will then be sorted alphabetically. Missing descriptive statistics or p-values which cannot be estimated will be reported as '-'.
- Unless otherwise noted, the percentage of subjects will be calculated as a proportion of the number of subjects assessed in the relevant treatment group (or overall) for the analysis set presented. Details about the selection of denominator will be described in footnotes or programming notes, as necessary.
- For categorical summaries (number and percentage of subjects) where a subject can be included in more than one category, a footnote or programming note will be added describing whether the subject is included in the summary statistics for all relevant categories or just 1 category as well as the selection criteria.
- Where a category with a subheading (such as system organ class) has to be split over more than one page, the subheading followed by '(cont)' will be printed at the top of each subsequent page. The overall summary statistics for the subheading will only be output on the first relevant page.

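### Do responder differences on observed data conflict with multiple imputation as the primary approach for mRS and NIHSS?

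*SAP*

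**What the plan says.** SAP 10.1.1 begins with a paragraph of summaries: responder counts and percentages by arm on observed ITT data, then "The difference of the proportions based on observed data of ITT between the treatment groups with the corresponding 95% confidence intervals". SAP 10.1.2 repeats this for NIHSS: "The difference of the proportions based on observed data of ITT between the treatment groups with the corresponding 95% CIs will be presented". In both sections a new paragraph then starts on the comparison between arms, with a chi-square test at each timepoint and further text that cannot be read. Both sections also contain a partly redacted pointer to 10.1.3.

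On missing values, SAP 8.3 states "Missing data will be imputed for the efficacy variables mRS and NIHSS as described in" Section 10.1, and SAP 10.1.3 states "The primary analysis approach for mRS and NIHSS efficacy endpoints will consider the multiple imputation (MI) of missing data". The opening text of SAP section 10 performs the mRS and NIHSS comparisons either after MI or by a second route whose description is cut off. For the remaining efficacy endpoints it plans no imputation, so that "summaries and statistical analysis will use the observed data within ITT only". SAP 10.1.4 adds: "The main analysis will be repeated on the PP and Completers populations as supportive analyses".

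SAP 8.1 and section 10 call all comparisons exploratory and descriptive. SAP section 7 declares estimands not applicable.

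**The concern.** The only readable responder differences with confidence intervals for mRS and NIHSS use observed data, while the approach named as primary fills in the missing values. The table convention in SAP 16.2.5.2 points the same way, since by default "the number of subjects in the analysis set for the treatment group who have an observation will be the denominator". Section 10 ties observed-data analysis to the other endpoints, which can be read as excluding mRS and NIHSS from it. SAP 10.1.4 repeats a main analysis without saying in readable text which difference belongs to it, and there is no estimand to settle the matter.

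The risk is that a report leads with one number while the primary approach supports another. If loss of late scores depends on arm and on early neurological status, the observed-data difference is biased, whereas MI that uses the early scores largely corrects this. With two differences available and neither labelled as the headline, someone could choose between them after unblinding.

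**Working it through.** **1. The passages side by side.** Sections 10.1.1 and 10.1.2 put the observed-data difference in the paragraph on summaries. The comparison between arms comes in a separate paragraph, and section 10 attaches MI to that comparison. Section 10.1.3 names MI as primary, and 10.1.4 follows it directly, so the main analysis repeated there is most naturally the one just described. The sentence in section 10 on the other endpoints says only that those are not imputed. It does not forbid observed-data summaries for mRS and NIHSS. Describing what was observed and comparing arms after MI is a coherent scheme.

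**2. What cannot be read.** Text breaks off or is redacted in section 10 after the mention of MI, in 10.1.1 and 10.1.2 after the chi-square test, in nearly all of 10.1.3, and in the index of tables. A pooled difference with its interval could stand in any of these places.

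**3. How much might be missing.** The plan gives no readable dropout figure; the text under SAP 4.3 (sample size) is not readable. The only guide is LT3001-201 in Protocol 5.3.
- Arm sizes: 3 subjects = 18.8% gives 16; 1 subject = 12.5% gives 8.
- Day-30 NIHSS responders: 46.67% = 7/15 and 14.29% = 1/7.
- Not counted: 1 of 16 and 1 of 8, so 2 of 24 = 8.3% (exact 95% CI 1.0% to 27.0%). One subject per arm is no evidence of an imbalance.
- Observed difference: 7/15 − 1/7 = 32.4 points. Counting both as non-responders: 7/16 − 1/8 = 31.3. Extremes: 7/16 − 2/8 = 18.8 and 8/16 − 1/8 = 37.5. That spread reflects how small that study was.

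**4. Size of the shift, in closed form.** Assume 100 per arm and true rates of 45% and 35%. Let a fraction *m* of an arm be missing, with missing subjects responding at *f* times the arm's rate *p*. The observed rate is *p*(1 − *mf*)/(1 − *m*). With *f* = 0.5:

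| Missing, active / placebo | Observed rates | Difference (true 10.0) |
|---|---|---|
| 10% / 10% | 47.5% and 36.9% | 10.6 |
| 5% / 15% | 46.2% and 38.1% | 8.1 |
| 15% / 5% | 49.0% and 35.9% | 13.0 |

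The full-data half-width is 1.96 × √(0.45×0.55/100 + 0.35×0.65/100) = 13.5 points. A threefold imbalance with halved response among the missing therefore moves the estimate by about 3 points. At 5% / 15% with *f* = 0.25, the difference is 7.1, also about 3 points off.

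**5. Size of the shift, by simulation.** Assumptions: 200 subjects, 43% response, no true difference, three binary stratification factors, missingness driven by an early score, 2,000 trials per scenario.

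| Missing by arm | Mean shift of observed-data difference (points) |
|---|---|
| 5% / 5% and 8.3% / 8.3% | 0 by symmetry, simulated at most 0.16 |
| 10% / 5% | 0.41 to 1.42 |
| 12.5% / 6.25% | 0.46 to 1.73 |

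The Monte Carlo standard error is at most 0.05. The observed-data half-width is 14.0 to 14.5 points, and its coverage is 93.8% to 97.3%. MI using the early score shifts by 0.03 to 0.09 in the unequal scenarios, but by 0.19 to 1.43 if its model omits that score. When missingness also depends on the unseen response, the observed-data shift is 1.41 to 2.31 and the MI shift 0.63 to 1.15.

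**The case for a change.** The best case for acting is that naming an approach is not the same as naming an estimate. Section 10.1.3 ranks MI first, but no readable sentence attaches a confidence interval to an MI-based responder difference. One or two sentences, using imputed data sets already planned, would fix the headline before unblinding. The two estimates can also visibly disagree: at 8.3% missing in each arm they differ by 2 points or more in 5.2% to 16.3% of simulated trials, and at 12.5% / 6.25% in 10.3% to 42.0%. Phase II responder differences, though descriptive, can inform later planning.

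Part of this stands. The readable text does not label the headline difference, and labelling the observed-data figure as a summary would do no harm. The rest does not make it a defect. The gap falls where text is redacted, so the remedy may duplicate what is already there. With equal missingness, disagreement in a single trial is chance rather than bias, and 2 points is small beside a half-width of 14. Both scales also give death a score (mRS 6, NIHSS 42, Protocol 11.1 and 11.2), so deaths need not be missing at all. LT3001-201 had one death per arm, so its 8.3% may overstate what to expect here. No readable decision rule depends on a single responder difference.

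**Conclusion.** The concern does not call for a change. The plan describes the observed data and names MI as primary; an analyst following it would report the observed-data difference as a summary and base the comparison on MI. What remains open is a label, possibly settled in redacted text.

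The likely shift is about 0 with equal missingness and 0.4 to 1.7 points with a twofold imbalance. It reaches 2.3 points in the non-random simulation and about 3 in the harshest closed-form cases, against a half-width of roughly 14. Coverage of the observed-data interval stayed near 95% in the simulations with missingness driven by the early score. The response rates, missingness and its link to early scores are all assumed, since the documents give none for this trial. Much heavier or more lopsided loss would make the choice matter more, but MI would still be the named primary approach. The endpoints are secondary and exploratory, and the primary safety endpoint is unaffected.
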